2.10 Describe your plans for ensuring data security

This study involves only minimum necessary data, in which only de-identified data will be reported. Data will be entered and stored in an HP secure RedCap database. All patients in the RedCap database will be identified only by their assigned study ID number. The database linking the patient MRN and ID number will be stored on a password-protected CCRC share drive that is only accessible to CCRC assigned staff. All electronic identifiers will be destroyed from Regions Hospital computers at the time of manuscript completion. There will not be paper data collection records for this study.

2.11. List the KEY variables that will be collected to support the study aims outlined in item 1.1. KEY variables include those used for:

- 1) achieving the study aims (outcomes, predictors, potential confounders),**
- 2) identifying the study population (for inclusion/exclusion criteria),**
- 3) describing the study population**

Please see an [Example of a Completed Table](#) and an [Example Data Dictionary](#).

Variable Name	Data Source (patient survey, EMR, claims, registry)	Purpose (sample identification, description, grouping variable, study endpoint, predictor, covariate)	Measurement Scale (binary, continuous)
Presenting INR (iSTAT and laboratory value)	EMR	Study endpoint	Continuous
Time of initial INR draw (iSTAT and laboratory value)	EMR	Variable	Continuous
INR at 15 minutes post-administration of 4FPCC	EMR	Study endpoint	Continuous
Dose of 4FPCC in IU	EMR	Study endpoint	Binary
Time to administration of 4FPCC in minutes	EMR	Study endpoint	Continuous
Administration of additional 4FPCC in fixed dose arm	EMR	Study endpoint	Binary
Thromboembolic events within 7 days	EMR	Study endpoint	Binary
Timing of thromboembolic event	EMR	Study endpoint	Continuous

Patient charge of 4FPCC in dollars	EMR	Study endpoint	Continuous
Institution cost of 4FPCC in dollars (cost per unit)	Biocare	Study endpoint	Continuous
Weight (kg) at presentation	EMR	Covariate	Continuous
Use of other reversal agents (vitamin K and FFP)	EMR	Covariate	Binary
Age	EMR	Covariate	Continuous
Indication for 4FPCC	EMR	Covariate	Binary
Attending Provider Specialty (i.e. emergency medicine, trauma, hematology/oncology, neurosurgery)	EMR	Covariate	Binary
Hospital unit (i.e. emergency department, SICU, MICU, etc.)	EMR	Covariate	Binary
Eligible patients not enrolled due to physician discretion	EMR	Covariate	Binary

2.12 Provide operational definitions of any variables listed above that aren't adequately described by the variable name above, and provide a brief background of any validated measurement scales listed above.

Thromboembolic events may include deep vein thrombosis, pulmonary embolism, ischemic stroke or transient ischemic event, or myocardial infarction.

Indication for 4FPCC may include, but will not be limited to, intracranial hemorrhage, gastrointestinal hemorrhage, ruptured abdominal aortic aneurysm, intrathoracic hemorrhage, spinal cord hemorrhage, neck hematoma, or other emergent surgical indication.

2.13 If you are collecting data elements besides those listed in Table 2.10 above, provide a justification for gathering the additional data.

N/A

Reminder: For chart review studies, a data collection form must be uploaded with your application listing variables collected and how they are recorded (chart review studies). Provided are links to two example chart review tools: [Word Chart Review Example](#) and [Excel Chart Review Example](#)

****3. ANALYSIS****

3.1 Describe the statistical methods that will be used to address the study aims. For each aim, this will usually include:

- Description of the sample used for the particular analysis
- The variables included in the specific analysis and their role in the analysis
- Numeric summaries computed (e.g., mean, standard deviation, proportion, correlation)
- A summary of data exploration and presentation activities (e.g., generating scatter plots, summary tables)
- Description of statistical tests (e.g., independent samples t-test, Mann-Whitney test), and models constructed (e.g., logistic regression)

Please see our [Examples of Statistical Methods](#).

Describe here:

Note: Please reference the area/pages of an established protocol if you are not writing your own analysis plan.

The analytic study population will consist of patients enrolled during the study period who meet the inclusion/exclusion criteria in Section 2.3 – namely, adults on long-term warfarin therapy who present to the ED with emergent bleeding, or who are in need of urgent invasive surgical procedures. The exposure of interest will be fixed vs. variable dose 4FPCC, to which eligible patients will be randomly assigned in a 1:1 ratio. To evaluate the success of randomization, we will summarize patient demographics and relevant clinical factors by 4FPCC dosing assignment group, and conduct appropriate statistical tests (Fisher's exact test for categorical variables; Wilcoxon test for continuous variables) to identify any differences in the distributions of these factors. If there are no significant differences ($p < 0.05$) found, we will assume successful randomization, and subsequent statistical analyses will not additionally account for covariates.

(Primary) Aim 1: Fixed vs. variable dose 4FPCC and anticoagulation reversal

To evaluate whether fixed dose 4FPCC is acceptably comparable to variable dosing with respect to anticoagulation reversal, as defined by a targeted INR of ≤ 1.5 , we will employ an active-controlled non-inferiority approach to analysis of a randomized trial [D'Agostino 2003]. In order to establish non-inferiority of fixed dosing, we will test the following null and alternative hypotheses:

- $H_0: F - V \leq M$ (Variable dosing is superior to fixed)
- $H_1: F - V > M$ (Fixed dosing is not inferior to variable)

where V = variable dosing, F = fixed dosing, and M = the non-inferiority margin.

Based on previous literature [D'Agostino 2003, Goldstein 2015] and the available study sample, we propose to set the non-inferiority margin M to -0.1. In other words, if the proportion of warfarin reversal among fixed dose patients is no worse than 10% less than the proportion of warfarin reversal among variable dosed patients, then we will reject the null hypothesis (superiority of variable dosing), and consider the fixed dose to be acceptably non-inferior to variable dosing.

Results to be reported for this aim will consist of the proportion of reversal for each group, the risk difference (RD; the proportion of reversal in fixed group minus the proportion of reversal in variable group), and the risk ratio (RR; the proportion of reversal in fixed group divided by the proportion of reversal in variable group), along with 95% confidence intervals and p-values as appropriate. Non-inferiority will be established if the lower bound of the RD is greater than the pre-specified margin M (-0.1). The primary analysis will use an intent to treat (ITT) approach (fixed vs. variable treatment assignment); however, we will also conduct supplemental analyses using an 'as treated' or 'per protocol' (PP) approach, in which we will compare patients' actual received dose (regardless of assignment) with respect to successful reversal of anticoagulation. We expect the PP approach to complement the primary ITT results, and will be informative particularly if there is non-trivial overlap in dosing by assignment group.

(Secondary) Aim 2: Fixed vs. variable dose 4FPCC and thromboembolic events

Study patients will be followed for 7 days post-administration of 4FPCC for thromboembolic events, as defined in Section 2.12. For this outcome, we will calculate and report the risk (proportion of patients experiencing an event in each group), RD, and RR, with 95% confidence intervals and p-values, as described in Aim 1. While we expect the risk of thromboembolic events to be lower in the fixed dose group, due to the limited number of anticipated thromboembolic events in the study population, the study will not specifically be powered to detect statistically significant differences by dosing group.

(Secondary) Aim 3: Fixed vs. variable dose 4FPCC and costs

Cost outcomes will be assessed for all study patients and compared by dosing assignment. Generalized linear regression models will be constructed to estimate the difference in cost attributable to dosing assignment (β estimate), along with 95% confidence intervals and p-values. Specifications of the statistical models constructed will be dictated by the empirical distribution of cost outcomes, which we anticipate will be non-normal. In this case, the negative binomial distribution or other modeling assumptions may be used as appropriate.

Sample size:

3.2 What is the estimated sample size(s) for the primary study analyses (per group for studies with different arms or comparison groups)?

Preliminary data from Regions Hospital identified 67 patients treated with 4FPCC from January 2015 through May 2016, suggesting that we can expect about 4 eligible patients per month. Thus for a 1-year study we anticipate 48 patients in our study population, with approximately 24 patients in each dosing group. We will request approval to enroll up to 60 patients as more may present to the Emergency Department compared to our historical data.

3.3 The sample size selected was (check all that apply):

	Based on data likely to be available during a specific time period (often based on data available in past periods)
	To conduct one or more specific analyses with adequate statistical power
	To achieve a specified level of precision in one or more key estimates
	Other (explain):

3.4 Explain your choice of the sample size selection you listed above:

Sample size for this study will directly depend on the number of eligible patients on warfarin who present to the ED with bleeding emergencies during the study period.

3.5 Describe your assumptions concerning data available for analysis (e.g. How many subjects will be randomized, possibly lost to follow-up or a procedure? What do you expect for survey response rates, and how much missing data do you expect?). Include information as it pertains to your study (human or animal).

Our primary assumptions regarding available data include: 1) successful enrollment of eligible patients into the study; 2) complete data collection for relevant study variables; and 3) an even distribution of random assignment (1:1).

Missing data should be minimal, as the relevant clinical measures under evaluation are routinely documented in this context.

We also expect loss to follow-up to be minimal, as the observation period for a given patient is very short (INR can be evaluated within 15 minutes of 4FPCC administration), and it will be unlikely for patients to leave the hospital prior to collection of relevant measures during an emergency care situation. Though it is possible patients may die during hospitalization, sufficient information should be available for these individuals to contribute to the analysis, with the possible exception of Aim 2 (thromboembolic events).

Power analysis

NOTE: If you are doing a descriptive study (i.e., aside from computing confidence intervals you are not using statistical tests, inferential statistical testing for group comparisons, or statistical models), please complete 3.6 and skip 3.7-3.8.

If you are conducting statistical tests, using statistical inference to compare groups, or are building statistical models, please skip 3.6 and complete 3.7-3.8. **Please see our Example Power Analysis.**

3.6 Provide a measure of the precision of your estimates for key study endpoints, (e.g., 95% confidence intervals on proportions or means), using actual expected estimates.

N/A

3.7 What level of differences observed in your primary endpoints would be considered clinically or practically significant?

As dictated by the active-controlled non-inferiority approach, we will consider the fixed dose of 4FPCC to be non-inferior to variable dosing if the proportion of anticoagulation reversal is no worse than the specified difference margin of -10%.

3.8 What is the power for your primary analysis (and the set of assumptions underlying it: hypothesis addressed, expected pattern of effects with justification for these expectations, analysis used, variables in the analysis, effect sizes, sample sizes, alpha level, one or two-sided test)?

Assuming available treatment group samples of N=24, a non-inferiority margin of -0.1, an alpha significance level of 0.05, an expected targeted reversal proportion in the variable dosing group of 0.77 (pooled estimate from 13 previous studies) [Khorsand 2015], and a true difference in proportions of 0, we will have 22% power to detect non-inferiority of fixed vs. variable dosing of 4FPCC.

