Given the emergent nature of need for care with this clinical population, randomization will need to happen quickly following the physician decision to use 4FPCC for bleeding reversal. The CCRC intern is in the emergency department 24/7 and is able to respond quickly to the needs of patients upon physician request. This study will utilize a permuted block randomization schedule to allow for equal allocation of subjects in each arm. Given that we expect to enroll 4 patients per month over a 1-year time period, allowing for a total sample size of 48 patients (24 per group), the randomization scheme will consist of 12 permuted blocks of four. Sealed envelopes with the dosing arm (fixed vs. weight-based) will be in the research file in the locked medication room located in Pod E. Pod E is the area of the emergency department reserved for the most acute patients and is where these patients will be treated. All interns have badge access to the medication room. A filing box containing documents specific to ED research is located in the medication room. Once the treating physician deems a patient eligible, the intern will retrieve the envelope from the medication room; open the envelope and the physician will enter the order. We do not anticipate that randomization will take more than 20-30 seconds and thus will not delay patient care or treatment.

Staff Training

CCRC Intern Group

[name] will train the CCRC intern group at the monthly intern dinner in January 2016. Training will involve a PowerPoint presentation reviewing the background and significance of this study as well as the aims and hypotheses. The interns will be trained on the full study protocol with emphasis on the inclusion and exclusion criteria. [name] will also review a mock patient for data abstraction to ensure that everyone is getting data points in the EMR from the same location. [name] will train interns on the randomization procedure.

ED Staff Training

- All attending physicians will be informed of the study at the monthly ED faculty meeting in January. [name] will lead this presentation and will answer any questions.
- Residents will be informed of the study during the monthly Resident Rounds in January. This is a monthly 4-hour meeting that is mandatory for all ED residents. [name] attends this meeting and will present the study to the residents.

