- ED nursing staff will be informed about the study during daily huddles in the Emergency Department. Huddles are held three times daily for the nursing staff so that all shifts are informed. CCRC staff will attend the huddles to inform nursing staff of the study and answer any questions. We have utilized this method of education in the past and it is the best way in which to reach all nursing staff. We will attend huddles for the two weeks prior to study start.

ED Pharmacy Staff

ED pharmacy staff will be fully trained on the protocol by [name] and [name]. [name] is a senior pharmacist in the emergency department and is the primary investigator on this study. [name] is a PGY-1 Pharmacy Resident at Regions Hospital and is a Co-Investigator on this study. Both [name] and [name] will participate in training the pharmacy group.

2.7 Describe any interventions that are used in this study.

	Not Applicable
--	----------------

Eligible patients will be randomized in a 1:1 fashion to receive either a fixed dose of 1500 IU or the FDA-approved variable dosing based on body weight and presenting INR. The FDA-approved variable dosing algorithm is as follows: initial INR 2-3.9: 25 IU/kg (maximum dose 2500 IU), initial INR 4-6: 35 IU/kg (maximum dose 3500 IU), and initial INR >6: 50 IU/kg (maximum dose 5000 IU). The patient weight will be obtained using a scale and documented by the treating RN.

Randomization will be initiated with the research team member notifying the attending physician of patient enrollment, and the physician placing the order that is immediately visible in EPIC to the IV pharmacist preparing the medication. The pharmacist will prepare the study medication as either the fixed or variable dose. Exact doses of 4FPCC administered may vary slightly from the calculated doses as the amount of 4FPCC differs based on the vials utilized. The doses are unable to be blinded by the research team, as the fixed dose will have less drug volume.

Following the randomization to study doses, the patient will be monitored for continued bleeding by the treating physician. If the patient receiving the 1500 IU fixed dose remains in a bleeding state and the INR remains above goal, an additional 500 IU may be administered at the physician's discretion to minimize bleeding and attempt to achieve hemostasis. If a

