patient does receive the additional 500 IU dose, the patient will be included in the intent-to-treat (ITT) analysis and considered a treatment failure for fixed dosing. (NOTE: this should be based on INR – not subjective assessment of bleeding)

All patients on chronic anticoagulation with warfarin who present with an emergent bleed or need for urgent surgery will obtain an initial INR value via the iSTAT point of care test and a laboratory INR. Due to urgent need for administration of 4FPCC, the laboratory INR may not be evaluated prior to randomization. After patient enrollment and randomization, the patient will receive the study medication and have a laboratory INR drawn 15 minutes post-administration. Obtaining a pre- and post-INR laboratory value is standard of care in the emergency department. The laboratory INRs will be utilized in all cases to evaluate the change in INR from pre- to post-administration of 4FPCC. The INRs will be collected and documented in the EMR by the treating RN. All patients enrolled in the study will be evaluated and identified via the EMR for development of a thromboembolic event within 7 days post 4FPCC administration. A 7-day follow-up period was chosen based on other studies evaluating a 4FPCC fixed dose [11,12]. Enrolled patients will be prospectively followed throughout admission with daily chart review to determine if a thromboembolic event occurred. The last patient progress note written within the 7-day follow-up period will be evaluated. This will allow us to include all patients who might have been discharged prior to the 7-day period, but were readmitted with a thromboembolic event.

2.8 Provide a brief, sequential, bullet-point description of the all the data collection activities you will conduct from start to finish (e.g., chart review, patient survey, follow-up visits, data pull from the electronic medical record, etc.) and who will conduct each. Please see our [Example of Data Collection Steps](#).

The current study will assess patient data among enrollees for the outcomes presented in section 1.1:

- 1) Treating physician will notify CCRC intern of potential study patient or the intern will notice the patient on the ED Track Board and notify the physician
- 2) Patient identification and inclusion/exclusion screening performed by the ED research intern or CCRC researcher
- 3) Physician approves the enrollment into the study

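### Covariate adjustment depends on baseline significance tests that miss imbalances of about half an SD at 24 per arm; prespecify one INR-adjusted risk difference instead

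*Combined protocol and SAP*

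**What the plan says.** Section 3.1 compares demographics and clinical factors between arms with Fisher's exact test for categorical factors and the "Wilcoxon test for continuous variables". If nothing reaches p<0.05, "we will assume successful randomization, and subsequent statistical analyses will not additionally account for covariates". The factors to be tested are not listed, and no model or selection rule is given for the case where one is significant. Under Aim 1 of the same section, the primary result is the difference in reversal proportions, fixed minus variable. The lower bound of its 95% interval is compared with -0.1, and no interval method is named.

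Four other places bear on this:

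- Section 2.6: "This study will utilize a permuted block randomization schedule to allow for equal allocation of subjects in each arm". The blocks are of four; stratification is not mentioned.
- Section 2.7: the comparator is "the FDA-approved variable dosing based on body weight and presenting INR", whereas the other arm receives one fixed dose.
- Section 2.7 also warns that "the laboratory INR may not be evaluated prior to randomization".
- Section 2.11: the row "Presenting INR (iSTAT and laboratory value" is labelled a study endpoint. Seven other variables are labelled covariates: weight, age, indication, other reversal agents, attending specialty, hospital unit, and "Eligible patients not enrolled due to physician discretion".

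**The concern.** A baseline p-value reflects sample size as much as imbalance, and it says nothing about how strongly the factor predicts the outcome. In a small trial, an imbalance large enough to move the risk difference (RD) by part of the 10-point margin can pass as evidence of successful randomization. In a correctly randomized trial a significant result is a chance finding by construction, yet here it would switch the analysis to one that nobody has defined.

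The covariate list in section 2.11 does not fill the gap. One entry (eligible patients not enrolled) cannot vary among enrolled patients. Another (vitamin K and FFP) can follow randomization. Seven terms are also far too many for the expected number of reversal failures, 48 × 0.23 ≈ 11. Presenting INR sets the dose in one arm but not the other, so it is a plausible predictor of reaching INR ≤1.5, yet it is not on the list.

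At stake is a false claim of non-inferiority when chance gives the fixed arm lower presenting INRs. The opposite imbalance makes the test too strict.

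**Working it through.** **Inputs.** 24 per arm (3.2, 3.8); control reversal 0.77, margin -0.1, alpha 0.05 (3.8); 95% interval (3.1, Aim 1); test threshold 0.05 (3.1). The documents give no association between INR and reversal. I assume odds ratios (OR) of 1.6 and 2.7 for failing to reverse per SD of log INR, acting either in both arms or in the fixed arm only. The second is at least as plausible, because the variable dose rises with INR.

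**1. The plan's own figure.** SE = √(2 × 0.77 × 0.23 / 24) = 0.1215 and 0.1/0.1215 = 0.823. At one-sided 0.05, Φ(0.823 − 1.645) = 20.6%; exact enumeration gives 22.0%, the stated power. At one-sided 0.025, which a two-sided 95% interval implies, Φ(0.823 − 1.960) = 12.8%; exact power is 12.1% with a score interval and 14.4% with Wald. The 95% decision rule makes 2.5% the benchmark below.

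**2. What passes the baseline test.** An observed 0.5 SD difference gives z = 0.5/√(2/24) = 1.73, p = 0.083. A t-test would need t(0.975, 46) × √(2/24) = 0.581 SD. The exact Wilcoxon test (size 4.83%) has no sharp cut. In 200,000 simulated trials the pass rates were:

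| Observed imbalance (SD) | Passes |
|---|---|
| 0.40–0.45 | 99% |
| 0.45–0.50 | 96% |
| 0.50–0.54 | 88% |
| 0.54–0.58 | 75% |
| 0.58–0.62 | 53% |
| 0.62–0.66 | 26% |

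Imbalances of at least 0.4 SD that pass occur in 12% of trials. With three independent continuous factors (assumed), at least one is significant in 1 − 0.9517³ = 14% of correctly randomized trials.

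**3. How far a passed imbalance moves the RD.** To first order the shift is p(1−p) × ln(OR) × 0.4 for a 0.4 SD imbalance with INR acting in both arms. For OR 1.6 this is 0.1771 × 0.470 × 0.4 = 3.3 points; for OR 2.7 it is 0.1771 × 0.993 × 0.4 = 7.0 points. Integrating over the INR distribution gives 3.2 and 6.0 points, or 1.6 and 2.9 if INR acts in the fixed arm only.

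**4. False non-inferiority at the margin (67% v 77%).** 160,000 trials were simulated per scenario. The conditional columns cover the 10.6% of trials that pass with fixed-arm INR 0.3–0.5 SD lower (about 17,000 trials, Monte Carlo SE about 0.15 points). The adjusted analysis is the one set out in the fix, including its fallback.

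| INR acts in | OR | Conditional: score | Conditional: Wald | Conditional: adjusted | Overall: score | Overall: Wald | Overall: adjusted |
|---|---|---|---|---|---|---|---|
| Fixed arm only | 1.6 | 3.1% | 3.8% | 2.6% | 2.4% | 2.9% | 2.4% |
| Fixed arm only | 2.7 | 4.1% | 5.1% | 3.2% | 2.5% | 3.0% | 2.5% |
| Both arms | 1.6 | 4.1% | 4.9% | 2.7% | 2.4% | 3.0% | 2.6% |
| Both arms | 2.7 | 5.5% | 6.6% | 2.8% | 2.4% | 3.0% | 2.6% |

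The mirror-image imbalance gives 0.4–1.7% with the score interval and 2.2–2.8% adjusted. A repeat run of 25,000 trials per scenario gave 3.3–6.2% v 2.7–3.3% conditionally and 2.4–2.5% v 2.5–2.7% overall. A skewed INR distribution and 30 per arm gave the same picture.

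**5. Where the fallback takes over.** It applies when either arm has at most 2 failures. At 77% reversal, the binomial probability for one arm of 24 is 0.0619, so 1 − (1 − 0.0619)² = 12%. At 71.8% v 77% it is 7.9%. At 85% it is 31–48%, at 90% 61–81% and at 95% 92–99%.

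**The case against.** - **The switch is partly inferred.** Aim 1 defines only the crude RD, and no sentence says an adjusted RD would replace it. This is so; but the sentence on covariates has no purpose unless a significant test changes something, and that change is undefined.
- **The remedy contains a switch of its own**, driven by the outcome. Near 77% reversal it operates in 7–12% of trials, more often than a single INR test fires (about 5%). What is fixed in advance is therefore the rule, not the estimator. The rule is objective and overall error stays at 2.4–2.6%. At 75% v 85% it is slightly higher than with the score interval (2.6–2.9% v 2.3–2.4%).
- **Weight also sets the variable dose.** Giving weight the same assumed ORs and conditioning on weight imbalance, the INR-adjusted analysis gave no protection: 3.6% and 4.1% v 3.5% and 4.1% unadjusted (fixed arm only), and 4.1% and 6.3% v 3.9% and 5.6% (both arms). This limit stands. About 11 expected failures justify one covariate with weight as a sensitivity analysis, but they do not show INR to be the stronger predictor.
- **A simpler repair exists**: delete the rule and keep the crude RD with a score interval. That removes the ambiguity and holds overall error, and at the margin the two analyses disagreed in only 0.7–1.8% of simulated trials. It leaves the conditional error in step 4.
- **The 2.5% benchmark is not stated.** Section 3.8 gives alpha 0.05 without sidedness, and its 22% matches one-sided 0.05. The decision rule nevertheless uses a 95% interval; the SAP should state the level.
- **Imbalances this large are uncommon.** At least 0.5 SD on one covariate occurs in 8–9% of trials, and about half of those pass. The claim concerns observed imbalances near 0.5 SD, not all larger ones.

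**Conclusion.** The concern holds. The rule should be changed before analysis, though it does not invalidate the trial. The plan lets baseline p-values decide whether the primary analysis is adjusted, leaves one branch undefined, and treats as an endpoint a pre-dose variable that sets the dose in one arm only. The crude RD is unbiased on average and overall type I error is essentially unaffected. The damage is conditional: in about one trial in ten, false non-inferiority is 3.1–5.5% with a score interval instead of 2.5%, and adjustment for INR brings it to 2.6–3.2%.

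The size rests on the assumed ORs and on reversal near the documents' relevant figures: 77% for planning (3.8) and 71.8% for INR <1.5 after 1500 IU (1.2). The 92–95% results for individual studies in sections 1.2 and 1.3 are for INR <2, although section 1.2 also cites more than 90% across studies with mixed targets. At 80% v 90% there is no gain: 3.3–4.8% with the score interval, 3.4–4.7% adjusted. Confidence in the magnitude is therefore moderate. The defect in the rule does not depend on it.

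**What to change.** Delete the significance rule, present baseline tables without tests, relabel presenting INR in section 2.11 as a baseline covariate, and put this in section 3.1:

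> The primary ITT risk difference (fixed minus variable) comes from a logistic regression of reversal on arm and log baseline INR, standardised over the ITT analysis population. The two-sided 95% CI uses the influence-function (robust) standard error multiplied by √(n/(n−3)) and a t quantile on n−3 df; its lower bound is compared with −0.10. If the fit does not converge, shows separation, or either arm has fewer than 3 reversal failures, the primary result is the unadjusted risk difference with a Miettinen-Nurminen 95% score interval. Baseline INR is the laboratory value from a sample drawn before 4FPCC is started, confirmed by the recorded draw time; if there is none, the iSTAT value is used. The unadjusted risk difference with its score interval is always reported alongside. Adding weight is a sensitivity analysis. Treatments given after randomization (vitamin K, FFP) are not covariates.

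The cost is SAP wording and a short, tested program. No new data are needed: section 2.11 already collects both INR values and "Time of initial INR draw (iSTAT and laboratory value". Near 77% reversal the variance of the RD changes by +3% if INR is not prognostic, by 0% and -10% at OR 1.6 and 2.7 in both arms, and by +2% and -0.5% in the fixed arm only. If INR acts only in the fixed arm, the adjusted RD is biased by up to 0.3 point at 77% and 0.5 point at 90%. Power at a true difference of 0 is 12.5–14.4% adjusted v 12.1–12.3% with the score interval, so the low power acknowledged in section 3.9 remains.

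If the sponsor prefers an unadjusted primary analysis, the significance rule must still go, and that single analysis and its interval method must be named in advance.

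### Two sentences word the non-inferiority decision without a confidence bound, which is inconsistent with the plan's lower-bound rule; the level of that bound is also left open

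*Combined protocol and SAP*

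**What the plan says.** All references are to section 3 (Analysis) of the combined protocol and SAP.

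- **Hypotheses and margin (3.1, Aim 1).** The null is F - V ≤ M, labelled "Variable dosing is superior to fixed". For the margin: "we propose to set the non-inferiority margin M to -0.1".
- **First decision wording (3.1, directly after the margin).** Offered as a restatement of the margin: if the fixed-dose proportion is "no worse than 10% less than the proportion of warfarin reversal among variable dosed patients, then we will reject the null hypothesis". No interval or bound appears.
- **Second decision wording (3.1, next paragraph).** "Non-inferiority will be established if the lower bound of the RD is greater than the pre-specified margin M (-0.1". The RD is defined as the fixed proportion minus the variable proportion and is reported "along with 95% confidence intervals and p-values as appropriate".
- **Third decision wording (3.7).** The form asks: "What level of differences observed in your primary endpoints would be considered clinically or practically significant". The answer is that the fixed dose will be considered non-inferior "if the proportion of anticoagulation reversal is no worse than the specified difference margin of -10" per cent. Again no bound is mentioned.
- **Power (3.8).** 24 per arm, margin -0.1, "an alpha significance level of 0.05" with sidedness not given, 0.77 reversal on variable dosing, true difference 0, power 22%.
- **Limitations (3.9).** Low power to reject the null is named as the primary limitation.

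**The concern.** The first and third wordings state a decision, to reject the null or to call the dose non-inferior, and compare a proportion with the margin. Read literally, they are met whenever the observed fixed-dose proportion is within 10 points of the observed variable-dose proportion. That takes no account of sampling error, which is large with 24 patients per arm. The second wording does take account of it.

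What is at stake is the primary conclusion. If there is truly no difference, the most likely result is an observed difference within 10 points whose interval extends below -0.10. The bound rule does not establish non-inferiority from that result, while the other two sentences, taken at face value, would allow the claim. Nothing in the plan calls such a result inconclusive. Treatment is unblinded, and section 6.3 says the results will influence whether the hospital adopts fixed dosing, so the rule should be beyond dispute before the data are seen.

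**Working it through.** **Inputs.** n = 24 per arm, M = -0.10, variable-dose rate 0.77, true difference 0 and alpha 0.05 (all item 3.8); 95% intervals (3.1). Sidedness and interval method are not stated, so both common levels are shown.

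**Step 1: reproduce the stated power.** Normal approximation at equality:

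SE = √(2 × 0.77 × 0.23 / 24) = 0.1215, and 0.10 / 0.1215 = 0.823.

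- One-sided 0.05: Φ(0.823 - 1.645) = Φ(-0.822) = 20.6%.
- One-sided 0.025 (the lower limit of a two-sided 95% interval): Φ(0.823 - 1.960) = Φ(-1.137) = 12.8%.

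Exact enumeration of two Binomial(24, 0.77) arms:

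| Interval | One-sided 0.05 | One-sided 0.025 |
|---|---|---|
| Wald | 22.0% | 14.4% |
| Newcombe | 22.3% | 12.5% |
| Score (Miettinen-Nurminen) | 20.0% | 12.2% |

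The stated 22% therefore matches a one-sided 0.05 bound (a two-sided 90% interval). It does not match the lower limit of the 95% intervals that section 3.1 reports.

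**Step 2: probability that each rule declares non-inferiority.** Sum of P(F = i) × P(V = j) over all (i, j) that meet the rule. The literal rule is i/24 - j/24 ≥ -0.10. The Wald rule is RD - z × √[p_F(1 - p_F)/24 + p_V(1 - p_V)/24] > -0.10, with z = 1.960 or 1.645.

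| True difference | Literal rule | Wald, two-sided 95% | Wald, one-sided 0.05 |
|---|---|---|---|
| 0 | 80.5% | 14.4% | 22.0% |
| -0.10 | 51.2% | 3.0% | 5.5% |
| -0.15 | 36.2% | 1.2% | 2.3% |
| -0.20 | 23.4% | 0.4% | 0.9% |

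A true difference of exactly -0.10 lies inside the null, so 51.2% is a false-positive rate. It stays between 51% and 53% for variable-dose rates from 0.60 to 0.947. At the 60-patient ceiling (30 per arm) it is 55.7% if an observed difference of exactly -0.10 passes and 44.2% if it does not.

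**Step 3: how often the wordings disagree.** Any result that meets the bound rule also meets the literal rule, so the disagreement is the difference between the two pass rates. At equality:

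- two-sided 95% Wald: 80.5% - 14.4% = 66.1%;
- one-sided 0.05 Wald: about 59% (80.5% - 22.0%).

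**Step 4: one concrete result.** With 19/24 reversals on variable dosing, the literal rule is met by 17/24 on fixed dosing (RD = -2/24 = -0.083). With 21/24, RD = 0.0833 and SE = 0.1069. The lower limit is 0.0833 - 1.645 × 0.1069 = -0.093, which passes, or 0.0833 - 1.960 × 0.1069 = -0.126, which fails. The two-sided 95% Wald rule needs 22/24 (0.125 - 1.960 × 0.1003 = -0.072).

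**The case against.** The strongest reply is that the plan already has an operative rule and these sentences only explain the margin. Section 3.1 sets formal hypotheses and says they will be tested. Only the lower-bound sentence names a statistic, a bound and a criterion. The first loose sentence follows directly from the choice of margin and is introduced as a restatement of it. Item 3.7 answers a question about what difference matters, refers to the non-inferiority approach, and takes its reference to observed differences from the form's own text. Neither sentence says that the proportions are the observed ones. The 22% power fits a bound-based test, whereas the literal rule would give about 80%, and naming low power as the main limitation would make little sense under the literal rule.

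This stands as evidence of intent, and it limits how serious the point is. It does not remove the inconsistency: both sentences state when non-inferiority will be concluded, and a reader has to infer from the power figure which wording governs.

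Three stronger readings might be inferred, and the documents do not support them:

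- *That the sponsor plans to decide on point estimates.* The evidence above points the other way.
- *That an inferior dose would pass about half the time in general.* The 51% applies at a true difference of exactly -0.10. The rate falls to 36% at -0.15 and 23% at -0.20.
- *That the 10% might be a relative margin.* M is defined on F - V and set at -0.1, the RD is a subtraction, and 3.7 calls it a difference margin, so the absolute reading is settled.

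**Conclusion.** The concern holds as an inconsistency in the wording of the primary decision rule, at moderate severity. Section 3.1's restatement of the margin and item 3.7 omit the confidence bound that section 3.1 requires. The bound rule is evidently intended. If the loose wording were applied as written, the false-positive rate at the margin would be 51%, against 3.0% (two-sided 95% Wald) or 5.5% (one-sided 0.05). With truly equal arms, the wordings would give different conclusions in 66% or 59% of trials respectively.

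These figures assume 24 per arm, a variable-dose rate of 0.77, independent binomial outcomes, and the literal rule applied to observed proportions.

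The check also shows that the level of the bound is not fixed. The 22% power corresponds to a one-sided 0.05 bound, while the reported intervals are 95%.

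**What to change.** Replace the restatement in 3.1 and the answer in 3.7 with one rule, for example:

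> Non-inferiority is concluded only if the lower confidence limit of the RD (fixed minus variable, in absolute percentage points) is above -0.10. An observed difference within 10 points whose interval crosses -0.10 is inconclusive.

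State the confidence level and the interval method in the same place, and make item 3.8 agree:

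- If the bound is the lower limit of the two-sided 95% interval already reported in 3.1, restate the power as about 14% (Wald) or about 12% (score).
- If the bound is one-sided 0.05, say so in 3.1 and 3.8. The 22% then stands with a Wald interval.

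The cost is two reworded sentences, one added specification and possibly a revised power figure, with no new data or procedures. The downside is that the two-sided 95% choice makes an already low stated power look less favourable. The change should be made before outcome data are seen, because choosing between the wordings afterwards would be open to challenge.
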